- Grade 3 solicited or unsolicited adverse event that is ongoing, whether or not it is improved or resolving. An unresolved or continuing Grade 1 or Grade 2 adverse event is permissible following the documented determination by the site principal investigator or appropriate sub-investigator, that it would not render study vaccination unsafe or interfere with the evaluation of adverse events or immunologic response.
- Grade 3 solicited or unsolicited adverse event that occurs in the 7 days following study vaccination, lasts for more than 24 hours without decreasing to a Grade 1 or Grade 2, and does not have an alternative etiology.
- Any laryngospasm, bronchospasm, or anaphylaxis within 1 day after administration of study product that is considered related to study product.
- Any generalized urticaria within 3 days after administration of study product that is considered related to study product.
- Serious adverse event related to the study vaccination.
- As deemed necessary by the site principal investigator or appropriate sub-investigator for noncompliance or other reasons.
- Subject refusal of further study vaccination.

- Termination of this trial.
- New information becomes available that makes further administration of the study vaccine unsafe.

Subjects who receive the first study vaccine but not the second vaccination will be encouraged to remain in this trial for follow-up, safety and immunogenicity assessments per [Appendix A: Schedule of Study Procedures and Evaluations](#). If the scheduled visit does not include collection of blood for safety or immunogenicity, the visit may be conducted by phone call/ electronic communication (e.g., email, text message) rather than in person continuing through approximately 6 months after the first study vaccination. See the protocol-specific Manual of Procedures (MOP) for alternate follow-up requirements.

Every attempt will be made to follow all adverse events, including solicited local site and systemic AEs, unsolicited non-serious adverse events, SAEs and MAAEs ongoing at the time of early withdrawal through resolution as per applicable collection times defined for the specific type of adverse event.

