6. GENERAL STATISTICAL CONSIDERATIONS

6.1. General Principles

Continuous variables will be summarized using descriptive statistics: n (non-missing sample size), mean, standard deviation, median, interquartile range, min, and max) unless otherwise specified. The frequency and percentages (based on the analysis population size) of observed levels will be reported for all categorical measures. In general, all data will be listed, sorted by study arm (1-3), subject, and when appropriate, by study visit number within subject. Unless otherwise specified, study arm labels shown in tables and figures will include the total population size relevant to the particular analysis. As subjects in all study arms will receive the same study product (ChAd3-EBO-Z) for the first vaccination (Table 1), results prior to the second vaccination (up to and including Day 8) will be presented jointly as “Study Arms 1, 2, and 3 (ChAd3)”. Post-second vaccination results will be presented separately for each of the three study arms.

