6.3. Analysis Populations

6.3.1. The Safety Analysis Population

The Safety Analysis population includes all subjects who received at least one study vaccination.

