6.3.3. The Per Protocol (PP) Analysis Population

The per protocol (PP) population includes all subjects in the ITT subset with the following exclusions:

- Data from all available visits for subjects found to be ineligible at baseline.
- Data from all visits subsequent to major protocol deviations, such as:
 - Second study vaccination not received,
 - Receipt of non-study licensed live vaccine within 30 days prior to or after each study vaccination,
 - Receipt of non-study licensed inactivated vaccine within 14 days prior to or after each study vaccination,
 - Receipt of oral or parenteral (including intraarticular) corticosteroids of any dose within 30 days prior to study vaccination.
 - Receipt of high-dose inhaled corticosteroids within 30 days prior to study vaccination.

- Receipt of chronic (defined as more than 14 days) immunosuppressants or other immune modifying drugs within 6 months of receipt of study vaccine.
- Data from any visit that occurs outside the pre-defined protocol window.
- In the case of mis-randomization, subjects will be analyzed according to the study product actually received.

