9. SAFETY EVALUATION

All safety analyses will be presented using the safety population. Any medical condition that is present at the time that the subject is screened will be considered baseline and not reported as an AE, unless it worsens in severity or increases in frequency during the study. When calculating the incidence of solicited and unsolicited adverse events (i.e., on a per subject basis), each subject will be counted once and any repetitions of solicited and unsolicited adverse events within a subject will be ignored; the denominator will be the number of subjects in the safety analysis population unless results are shown by dose in which case the denominator will be the number of subjects that received the respective dose.

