Myalgia	x	x.x	x.x, x.x	x	x.x	x.x, x.x	x	x.x	x.x, x.x	x	x.x	x.x, x.x	x	x.x	x.x, x.x	x	x.x	x.x, x.x	x	x.x	x.x, x.x
Headache	x	x.x	x.x, x.x	x	x.x	x.x, x.x	x	x.x	x.x, x.x	x	x.x	x.x, x.x	x	x.x	x.x, x.x	x	x.x	x.x, x.x	x	x.x	x.x, x.x
Nausea	x	x.x	x.x, x.x	x	x.x	x.x, x.x	x	x.x	x.x, x.x	x	x.x	x.x, x.x	x	x.x	x.x, x.x	x	x.x	x.x, x.x	x	x.x	x.x, x.x
Loss of Appetite	x	x.x	x.x, x.x	x	x.x	x.x, x.x	x	x.x	x.x, x.x	x	x.x	x.x, x.x	x	x.x	x.x, x.x	x	x.x	x.x, x.x	x	x.x	x.x, x.x
Any Local Symptom	x	x.x	x.x, x.x	x	x.x	x.x, x.x	x	x.x	x.x, x.x	x	x.x	x.x, x.x	x	x.x	x.x, x.x	x	x.x	x.x, x.x	x	x.x	x.x, x.x
Pain	x	x.x	x.x, x.x	x	x.x	x.x, x.x	x	x.x	x.x, x.x	x	x.x	x.x, x.x	x	x.x	x.x, x.x	x	x.x	x.x, x.x	x	x.x	x.x, x.x

Table 24: Number and Percentage of Subjects Experiencing Solicited Events with 95% Confidence Intervals by Symptom, Dose, and Treatment Group (Continued)

Symptom	Post Dose 1 Study Arm 1,2,3 ChAd3 (N=X)*			Post Dose 2 Study Arm 1 ChAd3+Placebo (N=X)			Post Dose 2 Study Arm 2 ChAd3+ChAd3 (N=X)			Post Dose 2 Study Arm 3 ChAd3+MVA-BN (N=X)			Post Either Dose Study Arm 1 ChAd3+Placebo (N=X)			Post Either Dose Study Arm 2 ChAd3+ChAd3 (N=X)			Post Either Dose Study Arm 3 ChAd3+MVA-BN (N=X)		
	n	%	95% CI†	n	%	95% CI†	n	%	95% CI†	n	%	95% CI†	n	%	95% CI†	n	%	95% CI†	n	%	95% CI†
Tenderness	x	x.x	x.x, x.x	x	x.x	x.x, x.x	x	x.x	x.x, x.x	x	x.x	x.x, x.x	x	x.x	x.x, x.x	x	x.x	x.x, x.x	x	x.x	x.x, x.x
Pruritis	x	x.x	x.x, x.x	x	x.x	x.x, x.x	x	x.x	x.x, x.x	x	x.x	x.x, x.x	x	x.x	x.x, x.x	x	x.x	x.x, x.x	x	x.x	x.x, x.x
Ecchymosis (Functional Grade)	x	x.x	x.x, x.x	x	x.x	x.x, x.x	x	x.x	x.x, x.x	x	x.x	x.x, x.x	x	x.x	x.x, x.x	x	x.x	x.x, x.x	x	x.x	x.x, x.x
Ecchymosis (Measurement Grade)	x	x.x	x.x, x.x	x	x.x	x.x, x.x	x	x.x	x.x, x.x	x	x.x	x.x, x.x	x	x.x	x.x, x.x	x	x.x	x.x, x.x	x	x.x	x.x, x.x
Erythema (Functional Grade)	x	x.x	x.x, x.x	x	x.x	x.x, x.x	x	x.x	x.x, x.x	x	x.x	x.x, x.x	x	x.x	x.x, x.x	x	x.x	x.x, x.x	x	x.x	x.x, x.x
Erythema (Measurement Grade)	x	x.x	x.x, x.x	x	x.x	x.x, x.x	x	x.x	x.x, x.x	x	x.x	x.x, x.x	x	x.x	x.x, x.x	x	x.x	x.x, x.x	x	x.x	x.x, x.x
Induration (Functional Grade)	x	x.x	x.x, x.x	x	x.x	x.x, x.x	x	x.x	x.x, x.x	x	x.x	x.x, x.x	x	x.x	x.x, x.x	x	x.x	x.x, x.x	x	x.x	x.x, x.x
Induration (Measurement Grade)	x	x.x	x.x, x.x	x	x.x	x.x, x.x	x	x.x	x.x, x.x	x	x.x	x.x, x.x	x	x.x	x.x, x.x	x	x.x	x.x, x.x	x	x.x	x.x, x.x

N = Number of subjects in the Safety Population who received the specified dose.

*: Subjects in treatment groups that received the same study product were analyzed jointly.

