14.3.5 Displays of Laboratory Results

14.3.5.2 Hematology Results

Table 35: Laboratory Results by Parameter, Maximum Severity, Study Day, and Treatment Group – Any Hematology Parameter

Study Visit Day	Treatment Group	None				Mild				Moderate				Severe			Missing			
		N	n	%	95% CI [†]	n	%	95% CI [†]	n	%	95% CI [†]	n	%	95% CI [†]	n	%	95% CI [†]	n	%	95% CI [†]
Baseline (First Vaccination)	Study Arm 1, 2, 3 ChAd3 (N=X)*	x	x	x.x	x.x – x.x	x	x.x	x.x – x.x	x	x.x	x.x – x.x	x	x.x	x.x – x.x	x	x.x	x.x – x.x	x	x.x	x.x – x.x
Day 8 (Second vaccination)	Study Arm 1, 2, 3 ChAd3 (N=X)*	x	x	x.x	x.x – x.x	x	x.x	x.x – x.x	x	x.x	x.x – x.x	x	x.x	x.x – x.x	x	x.x	x.x – x.x	x	x.x	x.x – x.x
Day 8 Post-Second Vaccination	Study Arm 1 ChAd3+Placebo (N=X)	x	x	x.x	x.x – x.x	x	x.x	x.x – x.x	x	x.x	x.x – x.x	x	x.x	x.x – x.x	x	x.x	x.x – x.x	x	x.x	x.x – x.x
	Study Arm 2 ChAd3+ChAd3 (N=X)	x	x	x.x	x.x – x.x	x	x.x	x.x – x.x	x	x.x	x.x – x.x	x	x.x	x.x – x.x	x	x.x	x.x – x.x	x	x.x	x.x – x.x
	Study Arm 3 ChAd3+MVA-BN (N=X)	x	x	x.x	x.x – x.x	x	x.x	x.x – x.x	x	x.x	x.x – x.x	x	x.x	x.x – x.x	x	x.x	x.x – x.x	x	x.x	x.x – x.x
Day 22 Post-Second Vaccination	Study Arm 1 ChAd3+Placebo (N=X)	x	x	x.x	x.x – x.x	x	x.x	x.x – x.x	x	x.x	x.x – x.x	x	x.x	x.x – x.x	x	x.x	x.x – x.x	x	x.x	x.x – x.x
	Study Arm 2 ChAd3+ChAd3 (N=X)	x	x	x.x	x.x – x.x	x	x.x	x.x – x.x	x	x.x	x.x – x.x	x	x.x	x.x – x.x	x	x.x	x.x – x.x	x	x.x	x.x – x.x
	Study Arm 3 ChAd3+MVA-BN (N=X)	x	x	x.x	x.x – x.x	x	x.x	x.x – x.x	x	x.x	x.x – x.x	x	x.x	x.x – x.x	x	x.x	x.x – x.x	x	x.x	x.x – x.x
Day 29 Post-Second Vaccination	Study Arm 1 ChAd3+Placebo (N=X)	x	x	x.x	x.x – x.x	x	x.x	x.x – x.x	x	x.x	x.x – x.x	x	x.x	x.x – x.x	x	x.x	x.x – x.x	x	x.x	x.x – x.x
	Study Arm 2 ChAd3+ChAd3 (N=X)	x	x	x.x	x.x – x.x	x	x.x	x.x – x.x	x	x.x	x.x – x.x	x	x.x	x.x – x.x	x	x.x	x.x – x.x	x	x.x	x.x – x.x
	Study Arm 3 ChAd3+MVA-BN (N=X)	x	x	x.x	x.x – x.x	x	x.x	x.x – x.x	x	x.x	x.x – x.x	x	x.x	x.x – x.x	x	x.x	x.x – x.x	x	x.x	x.x – x.x
Max Severity Post Baseline	Study Arm 1 ChAd3+Placebo (N=X)	x	x	x.x	x.x – x.x	x	x.x	x.x – x.x	x	x.x	x.x – x.x	x	x.x	x.x – x.x	x	x.x	x.x – x.x	x	x.x	x.x – x.x
	Study Arm 2 ChAd3+ChAd3 (N=X)	x	x	x.x	x.x – x.x	x	x.x	x.x – x.x	x	x.x	x.x – x.x	x	x.x	x.x – x.x	x	x.x	x.x – x.x	x	x.x	x.x – x.x
	Study Arm 3 ChAd3+MVA-BN (N=X)	x	x	x.x	x.x – x.x	x	x.x	x.x – x.x	x	x.x	x.x – x.x	x	x.x	x.x – x.x	x	x.x	x.x – x.x	x	x.x	x.x – x.x

N = Number of subjects in the Safety Population

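### Post-boost laboratory tables use the whole Safety Population as N, so a subject who missed the boost would stay in the randomised arm's denominator

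*SAP*

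**What the plan says.** SAP 6.3.1 defines the base for safety: "The Safety Analysis population includes all subjects who received at least one study vaccination". SAP 6.1 sets the rule for percentages: "The frequency and percentages (based on the analysis population size) of observed levels will be reported for all categorical measures".

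The laboratory shells follow from this. Tables 35, 36 and 37 pool the three arms at baseline and Day 8. They then give separate rows for each arm at Days 8, 22 and 29 after the second vaccination, plus a maximum-severity row covering all time after baseline. The footnote under Table 35 reads "N = Number of subjects in the Safety Population", and Tables 36 and 37 say the same. Figure 13 states no population.

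The solicited-event shells differ. Table 24 has "N = Number of subjects in the Safety Population who received the specified dose", and Tables 25 and 26 carry an equivalent note.

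SAP 9 contains a by-dose rule. It begins "When calculating the incidence of solicited and unsolicited adverse events (i.e., on a per subject basis" and sets the Safety Population as denominator "unless results are shown by dose in which case the denominator will be the number of subjects that received the respective dose". Laboratory events are not named in it.

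A rule on product received exists only for the per-protocol population, in SAP 6.3.3: "In the case of mis-randomization, subjects will be analyzed according to the study product actually received".

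Protocol 5.4.3 provides for people who miss the boost: "Subjects who receive the first study vaccine but not the second vaccination will be encouraged to remain in this trial". Their follow-up includes safety assessments under Appendix A.

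**The concern.** Laboratory adverse events are one of the four primary outcomes (Protocol 3.2.1). A row headed as post-second vaccination should describe people who had that vaccination. Under the stated footnotes it would describe everyone randomised to the arm who had at least the prime, so a subject who never received the boost would count towards the boost arm's percentage. A subject given the wrong boost has no defined place in these tables at all, because the only rule on actual product governs per-protocol analyses.

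The SAP already applies the right principle to solicited events. As it stands, the two primary safety displays for the same arm and period could rest on different sets of subjects, with nothing telling the reader so.

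**Working it through.** **Can prime-only subjects reach these rows?** Protocol 8.2.1 schedules safety laboratories on Days 1, 8, 15, 29 and 36 after the prime. With the boost on Day 8, Days 15, 29 and 36 are Days 8, 22 and 29 after the boost (15 − 7, 29 − 7, 36 − 7). Prime-only subjects are asked to stay for safety follow-up, so they can have these samples, and Tables 35 to 37 offer no prime-only row. Table 13 lists non-receipt of the second vaccination as an exclusion reason under these same visit labels, so the SAP foresees such subjects at these visits. It removes them for the per-protocol analysis. No matching step exists for the laboratory tables.

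**What is not specified.** The SAP does not say whether such a subject's later results go in the post-second-vaccination rows, are counted as missing, or are left out.

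**Size in Table 35.** The SAP gives no figure to reproduce. Inputs: 20 two-dose subjects per arm (Protocol 5.4.5, which permits replacement to reach that number), and exact Clopper-Pearson intervals (Table 35). The number of prime-only subjects per arm, k, is not in the documents; I assume 1 to 3. With x events among the 20 boosted and j abnormal among the k, the rate moves from x/20 to (x + j)/(20 + k). The interval limits are the 2.5% quantile of Beta(x, n − x + 1) and the 97.5% quantile of Beta(x + 1, n − x), with the lower limit 0 when x = 0.

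| Boosted only | k | Prime-only normal or missing | Prime-only all abnormal |
|---|---|---|---|
| 0/20 = 0% (0–16.8) | 1 | 0/21 = 0% (0–16.1) | 1/21 = 4.8% (0.1–23.8) |
| 0/20 = 0% (0–16.8) | 2 | 0/22 = 0% (0–15.4) | 2/22 = 9.1% (1.1–29.2) |
| 0/20 = 0% (0–16.8) | 3 | 0/23 = 0% (0–14.8) | 3/23 = 13.0% (2.8–33.6) |
| 2/20 = 10.0% (1.2–31.7) | 1 | 2/21 = 9.5% (1.2–30.4) | 3/21 = 14.3% (3.0–36.3) |
| 2/20 = 10.0% (1.2–31.7) | 2 | 2/22 = 9.1% (1.1–29.2) | 4/22 = 18.2% (5.2–40.3) |
| 2/20 = 10.0% (1.2–31.7) | 3 | 2/23 = 8.7% (1.1–28.0) | 5/23 = 21.7% (7.5–43.7) |

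**Bound for one subject.** The upward shift is (x + 1)/21 − x/20 = (20 − x)/420, largest at x = 0, which is 4.8 points. The downward shift is x/20 − x/21 = x/420, which is 0.5 points at x = 2.

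**Tables 36 and 37.** These give means and medians of available values, so a missing result does not dilute them. A prime-only value v placed in the row changes a mean m of 20 to (20m + v)/21.

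**Maximum-severity row.** The notes under Tables 35 and 36 define it over any time after baseline, including unscheduled tests. It therefore takes in the Day 8 sample, which Protocol 7.3.2 has drawn before the boost. Prime-period abnormalities thus appear by arm in this row for every subject, boosted or not.

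**The case against.** The strongest reply is that this is a footnote mismatch in descriptive tables, with an effect that may never arise. Several parts of it stand.

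- Table 35 has its own N column and a missing category in each row, and SAP 6.1 says arm labels carry the population size relevant to the analysis. The follow-up visits are timed from the second vaccination, which a prime-only subject lacks. Such subjects may end up as missing.
- The arm labels name the regimen. SAP 4.2 explains that the placebo-boost arm is there to account for prime effects lasting beyond Day 8, so some carry-over is expected in every arm.
- A careful reader could recover the facts. Tables 33 and 34 list each abnormal result with its study day and relationship to treatment, Listing 8 gives receipt of the boost, and Table 14 counts those who had both doses.

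These points limit the harm. They do not align the footnotes or supply a rule on product received, and a subject counted as missing still enlarges the denominator.

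Two stronger readings are tempting, and the documents do not support them. A reader might infer that the plan charges prime-related abnormalities to a product that was not given. That requires a prime-only subject, a later sample, an abnormality, and a visit mapping the SAP does not state. A reader might also argue that boosts are withheld selectively, so unboosted subjects are those most likely to have abnormal laboratories. Protocol 5.4.3 does withhold the boost for some Grade 3 and related events, but also for refusal, pregnancy and noncompliance. The first scheduled laboratory sample after the prime is drawn on Day 8 just before the boost, and Protocol 7.3.2 requires only the pregnancy result to be known first. Protocol 2.3.1 describes earlier blood-count changes as transient and mostly Grade 1.

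**Conclusion.** The inconsistency holds. As written, any prime-only subject would be in the post-boost laboratory denominator of the randomised arm, and neither SAP 6.3.1 nor SAP 9 assigns laboratory results by product actually received. Denominator inclusion follows from the footnotes; a misplaced abnormality in the numerator is only possible.

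The size is modest. With 20 boosted subjects in an arm, one prime-only subject moves a Table 35 rate by at most about 5 percentage points, up or down, against exact intervals already 17 to 30 points wide for 0 or 2 events in 20. If every subject received the assigned boost, nothing changes in the by-visit rows. The documents give no number of unboosted or wrongly boosted subjects, so no probability can be attached. Assuming 2% to 5% miss the boost gives 1 − 0.98^20 = 33% to 1 − 0.95^20 = 64%, but those rates have no source, and the result is only the chance of at least one such subject in an arm of 20, not of a misattributed finding.

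The maximum-severity row is the more certain route by which prime-period results appear under boost-arm labels, since it does not depend on anyone missing the boost.

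**What to change.** 1. In Tables 35 to 37, footnote the post-second-vaccination rows as the Safety Population who received the second vaccination, matching Table 24.
2. Add to SAP 6.3.1 that safety results after the second vaccination are summarised by the product actually received at that vaccination.
3. Show the Day 15, 29 and 36 laboratory results of prime-only subjects in a separate row or listing, and state how their visits are labelled.
4. Split the maximum-severity row into before and after the second vaccination. Protocol 11.4.2 asks for a maximum over all post-vaccination visits, so if that overall row is kept, label it as covering the whole regimen.
5. Give Figure 13 the same population, since it now states none.

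The cost is a few more rows and footnotes in the table shells. No new data are needed.

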4.5.1. Safety Variables

Safety will be assessed by the occurrence of:

1. Serious adverse events and MAAEs occurring from the time of study vaccination through approximately 6 months after the first study vaccination.
2. Solicited Adverse Events – reactogenicity events occurring from the time of study vaccination through 7 days after each study vaccination:
 - a) Local AEs including pain, tenderness, erythema (redness), induration (hardness/swelling), ecchymosis (bruising) and pruritis (itching).
 - b) Systemic AEs including fever, feverishness (chills, shivering, sweating), fatigue (tiredness), malaise (general unwell feeling), myalgia (body aches/muscular pain), nausea, loss of appetite and headache.
3. Clinical safety laboratory adverse events occurring from the time of study vaccination through approximately 28 days after the second vaccination. Parameters to be evaluated include WBC, Hgb, platelet count, ANC, sodium, potassium, Creatinine, BUN (BUN will be obtained only if creatinine is above the normal range), and ALT.
4. Unsolicited Adverse Events – study vaccine-related non-serious adverse events occurring from the time of study vaccination through approximately 28 days after the second study vaccination.

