9.6. Clinical Laboratory Evaluations

Clinical safety laboratory adverse event gradings are presented in [Table 9](#) and [Table 10](#). Safety laboratory parameters and toxicity grade criteria are summarized in [Table 9](#) and [Table 10](#). Unscheduled or repeated follow-up tests for medical or safety reasons will be listed but excluded from per-visit tabular and graphical summaries. These results will be included when summarizing maximum response from baseline.

For baseline laboratory results that are abnormal according to the local laboratory reference range (see protocol Appendix C) and fall within Grade 1 toxicity table range, these will not be considered laboratory adverse event (AE) and will thus not be graded. However, if baseline clinical labs fall within Grade 1 range, then a laboratory AE is reported only if the value changes such that it falls into Grade 2 or higher when subsequent safety laboratory testing is done.

Listings of abnormal laboratory results will be provided as shown in [Table 33](#) and [Table 34](#). For each laboratory parameter, the following summaries will be generated for each treatment group:

- Laboratory AEs from the time of first study vaccination through approximately 28 days after the second vaccination will be summarized by severity grade (none, mild, moderate, severe) for each laboratory visit using percentages and exact two-sided 95% CIs ([Table 35](#)).
- A tabular summary of descriptive statistics including the mean, standard deviation, median, minimum, and maximum for per-visit results ([Table 36](#)).
- A tabular summary of descriptive statistics including the mean, standard deviation, median, minimum, and maximum for fold change compared to pre-vaccination ([Table 37](#)).
- A graphical summary of change from baseline ([Figure 13](#)).

[Listing 13](#) and [Listing 14](#) will provide a complete listing of individual clinical laboratory results.

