Note: The “Max Post Baseline” rows indicate the maximum severity experienced by each subject at any time point post baseline, including unscheduled assessments.

*: Subjects in treatment groups that received the same study product were jointly analyzed.

†: Based on Clopper-Pearson.

Generate this table for each hematology laboratory parameter: Absolute Neutrophil Count, Hgb (Decrease), Platelet (Decrease), Platelet (Increase), WBC (Decrease), WBC (Increase) and chemistry parameter: Any Chemistry Parameter, ALT (Increase), BUN, Creatinine (Increase), Potassium (High), Potassium (Low), Sodium (High), Sodium (Low).

Table 36: Laboratory Summary Statistics by Parameter, Study Day, and Treatment Group – Absolute Neutrophil Count (K/mcL)

Time Point	Treatment Group	N	Mean	Standard Deviation	Median	Min, Max
Baseline (First Vaccination)	Study Arm 1,2,3 ChAd3 (N=X)*	x	x.x	x.x	x	x, x
Day 8 (Second Vaccination)	Study Arm 1,2,3 ChAd3 (N=X)*	x	x.x	x.x	x	x, x
Day 8 Post-Second Vaccination	Study Arm 1 ChAd3+Placebo (N=X)	x	x.x	x.x	x	x, x
	Study Arm 2 ChAd3+ChAd3 (N=X)	x	x.x	x.x	x	x, x
	Study Arm 3 ChAd3+MVA-BN (N=X)	x	x.x	x.x	x	x, x
Day 22 Post-Second Vaccination	Study Arm 1 ChAd3+Placebo (N=X)	x	x.x	x.x	x	x, x
	Study Arm 2 ChAd3+ChAd3 (N=X)	x	x.x	x.x	x	x, x
	Study Arm 3 ChAd3+MVA-BN (N=X)	x	x.x	x.x	x	x, x
Day 29 Post-Second Vaccination	Study Arm 1 ChAd3+Placebo (N=X)	x	x.x	x.x	x	x, x
	Study Arm 2 ChAd3+ChAd3 (N=X)	x	x.x	x.x	x	x, x
	Study Arm 3 ChAd3+MVA-BN (N=X)	x	x.x	x.x	x	x, x
Max Severity Post Baseline	Study Arm 1 ChAd3+Placebo (N=X)	x	x.x	x.x	x	x, x
	Study Arm 2 ChAd3+ChAd3 (N=X)	x	x.x	x.x	x	x, x
	Study Arm 3 ChAd3+MVA-BN (N=X)	x	x.x	x.x	x	x, x

N = Number of subjects in the Safety Population.

Note: The “Max Post Baseline” rows indicate the maximum severity experienced by each subject at any time point post baseline, including unscheduled assessments.

*: Subjects in treatment groups that received the same study product were jointly analyzed.

Generate this table for each hematology laboratory parameter: Absolute Neutrophil Count (K/mcL), Hgb (g/dL), Platelet count (K/mcL), WBC (K/mcL) and chemistry parameter: ALT (unit/L), BUN (mg/dL), Creatinine (mg/dL), Potassium (mmol/L), and Sodium, (mmol/L).

Table 37: Laboratory Summary Statistics by Parameter, Study Day, and Treatment Group – Fold Change in Absolute Neutrophil Count (K/mcL) Relative to Pre-First Vaccination

Time Point	Treatment Group	N	Mean	Standard Deviation	Median	Min, Max

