Day 8 (Second Vaccination)	Study Arm 1,2,3 ChAd3 (N=X)*	x	x.x	x.x	x.x	x.x, x.x
Day 8 Post-Second Vaccination	Study Arm 1 ChAd3+Placebo (N=X)	x	x.x	x.x	x.x	x.x, x.x
	Study Arm 2 ChAd3+ChAd3 (N=X)	x	x.x	x.x	x.x	x.x, x.x
	Study Arm 3 ChAd3+MVA-BN (N=X)	x	x.x	x.x	x.x	x.x, x.x
Day 22 Post-Second Vaccination	Study Arm 1 ChAd3+Placebo (N=X)	x	x.x	x.x	x.x	x.x, x.x
	Study Arm 2 ChAd3+ChAd3 (N=X)	x	x.x	x.x	x.x	x.x, x.x
	Study Arm 3 ChAd3+MVA-BN (N=X)	x	x.x	x.x	x.x	x.x, x.x
Day 29 Post-Second Vaccination	Study Arm 1 ChAd3+Placebo (N=X)	x	x.x	x.x	x.x	x.x, x.x
	Study Arm 2 ChAd3+ChAd3 (N=X)	x	x.x	x.x	x.x	x.x, x.x
	Study Arm 3 ChAd3+MVA-BN (N=X)	x	x.x	x.x	x.x	x.x, x.x
Max Severity Post Baseline	Study Arm 1 ChAd3+Placebo (N=X)	x	x.x	x.x	x.x	x.x, x.x
	Study Arm 2 ChAd3+ChAd3 (N=X)	x	x.x	x.x	x.x	x.x, x.x
	Study Arm 3 ChAd3+MVA-BN (N=X)	x	x.x	x.x	x.x	x.x, x.x

N = Number of subjects in the Safety Population.

*: Subjects in treatment groups that received the same study product were jointly analyzed.

Generate this table for each hematology laboratory parameter: Absolute Neutrophil Count (K/mcL), Hgb (g/dL), Platelet count (K/mcL), WBC (K/mcL) and chemistry parameter: ALT (unit/L), BUN (mg/dL), Creatinine (mg/dL), Potassium (mmol/L), and Sodium (mmol/L).

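### BUN is tested only when creatinine is above normal, but the SAP summarises it like a routine analyte, so its fold changes and means come from selected subjects and its rates use the wrong denominator for those tested

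*SAP*

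**What the plan says.** SAP 4.5.1 lists BUN among the safety laboratory parameters with a condition: "BUN will be obtained only if creatinine is above the normal range". Protocol sections 8.2.1 and 9.1 carry the same condition.

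SAP 9.6 makes no exception for it: "For each laboratory parameter, the following summaries will be generated for each treatment group". The programming notes then name BUN each time:

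- Table 35 (severity grade by visit, with Clopper-Pearson intervals) is to be repeated for "Any Chemistry Parameter, ALT (Increase), BUN, Creatinine (Increase" and the remaining chemistry parameters. Its footnote reads "N = Number of subjects in the Safety Population". The shell has a Missing category with its own count, percentage and interval.
- Table 36 (per-visit descriptive statistics), Table 37 (fold change relative to the pre-first-vaccination value) and Figure 13 (mean fold change) each list "chemistry parameter: ALT (unit/L), BUN (mg/dL), Creatinine (mg/dL".

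The general denominator rule in SAP 6.1 is: "The frequency and percentages (based on the analysis population size) of observed levels will be reported for all categorical measures". SAP 6.5 leaves missing values missing. Neither document has a rule for a test that is omitted by design. There is no denominator based on the number tested, and nothing is said about an absent Day 1 BUN.

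**The concern.** For a routinely drawn analyte, a missing value is an occasional accident. For BUN it is the planned outcome whenever creatinine is normal, so whether a value exists depends on renal status at that visit. A summary that ignores this describes whoever happened to be selected.

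Three kinds of output are affected. The fold change leaves out the subjects in whom a BUN change would be of most interest, those whose creatinine first rises after vaccination. The per-visit means can move between visits or arms because different subjects were tested. The severity percentages divide by subjects who had no test. Laboratory adverse event frequency is a primary outcome, so the BUN rows would enter the primary safety tables populated and normal-looking, with nothing to tell the reader how they arose.

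**Working it through.** **Inputs.** 20 subjects per arm and 60 in total (protocol Table 1, SAP Table 1). Table 35 pools the arms at Day 1 and Day 8 and separates them afterwards. Intervals are two-sided 95% Clopper-Pearson. The laboratory baseline is Day 1 before the first vaccination (notes to SAP Tables 9 and 10). The upper reference limit for creatinine is 1.10 mg/dL in men and 0.80 in women, and the eligibility upper limits in protocol Appendix C are 1.3 and 1.2. The shells are empty and no precision target is stated, so the plan has no figure to reproduce.

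**Fold change (Table 37, Figure 13).** The ratio is BUN at the visit divided by BUN on Day 1, and each term exists only if creatinine was high at that time.

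| Creatinine on Day 1 | Creatinine at later visit | BUN fold change |
|---|---|---|
| normal | normal | none (neither value) |
| normal | high | none (no Day 1 value) |
| high | normal | none (no later value) |
| high | high | available |

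Only the last row contributes. Because Appendix C admits creatinine above the reference limit, that row can be populated, so the output is selective but not necessarily empty. This step needs no assumption about how many subjects are tested.

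**Means (Table 36).** The mean at each visit is taken over subjects with high creatinine at that visit. Those sets need not be the same subjects from visit to visit.

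**Rates (Table 35).** For x graded results among n subjects, the lower limit is the 0.025 quantile of Beta(x, n − x + 1) and the upper limit is the 0.975 quantile of Beta(x + 1, n − x). With x = 0 the lower limit is 0 and the upper limit is 1 − 0.025^(1/n). For n = 20 this is 1 − 0.8316 = 16.8%. As a check, (1 − 0.1684)^20 = 0.025.

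The number tested in an arm, m, is not in the documents. The values below are assumptions that span the range.

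| Denominator | 0 graded: upper limit | 1 graded: rate (95% CI) |
|---|---|---|
| 20 (as planned) | 16.8% | 5.0% (0.1–24.9) |
| m = 2 | 84.2% | 50.0% (1.3–98.7) |
| m = 5 | 52.2% | 20.0% (0.5–71.6) |
| m = 10 | 30.8% | 10.0% (0.3–44.5) |
| m = 18 | 18.5% | 5.6% (0.1–27.3) |

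The ratio of upper limits with no graded result is 84.2/16.8 = 5.0 at m = 2, 52.2/16.8 = 3.1 at m = 5, 30.8/16.8 = 1.8 at m = 10 and 18.5/16.8 = 1.1 at m = 18. For the pooled Day 8 row the limit is 6.0% on 60, against 45.9% (m = 6), 26.5% (m = 12) and 11.6% (m = 30).

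**What a row would show.** Suppose 3 of 20 are tested and none is graded. Table 35 prints None 3/20 = 15%, Missing 17/20 = 85%, and each graded category 0/20 with an upper limit of 16.8%. On the 3 tested, that limit is 70.8%.

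**The case against.** The strongest reply is that Table 35 already shows untested subjects. They fall under Missing, and SAP 6.5 forbids imputing them as None. A reader who infers that untested subjects are counted as normal would be wrong. This stands, but it does not settle the matter. The graded percentages and intervals still use the full population, and Missing mixes tests not called for with samples that were lost.

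Second, 0/20 with an upper limit of 16.8% is a valid exact interval for the share of all vaccinated subjects with a recorded graded BUN. That is correct. The interval is too narrow only when read as a rate among those tested. The interval on m in turn describes only subjects with high creatinine, so it is not an estimate of a BUN effect in the arm.

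Third, a reader might infer that hardly anyone will be tested and the intervals will be far too narrow. The documents do not support that. Entry is allowed with creatinine up to 1.2 mg/dL in women against a reference limit of 0.80, and up to 1.3 in men against 1.10, so m need not be small. At m = 18 the difference is slight.

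Fourth, a reader might infer that a renal signal would be lost. It would not. Creatinine is a scheduled safety test in every subject and has its own Table 35 to 37 output. Any BUN it triggers is graded, and BUN results remain in the planned listings (Table 33, Listing 14).

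**Conclusion.** The point holds as a minor one. The SAP applies routine-analyte summaries to a test that is conditional by design. The fold-change part is certain on the documents' own rules: Table 37 and Figure 13 can use only subjects with high creatinine both on Day 1 and at the later visit, and every new post-vaccination rise drops out. The selection behind the Table 36 means follows from the same rule.

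The Table 35 part depends on interpretation and on m. As rates among those tested, the planned percentages are diluted and the intervals too narrow. With no graded result in an arm of 20, the upper limit is understated by a factor between about 5 (m = 2) and about 1.1 (m = 18). Where in that range the trial falls cannot be said from the documents.

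The consequence is confined to one analyte in a trial with no formal hypothesis.

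**What to change.** In SAP 9.6 and the programming notes:

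- Remove BUN from the parameter lists for Table 36, Table 37 and Figure 13.
- In Table 35, print the number of subjects with a BUN result at each visit, and base the BUN percentages and exact intervals on that number.
- In the same table, show *not done per protocol* separately from Missing.
- Add a footnote that BUN testing was triggered by creatinine above normal, so the rate describes only those subjects.
- Leave the BUN listings (Table 33, Listing 14) as planned.

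Restricting Table 37 and Figure 13 to subjects with a Day 1 BUN, with a footnote, would make the selection visible but would still omit the new rises, so removal is cleaner. The cost is SAP wording and table programming, with no new data and no change to trial conduct. The downside is wider BUN intervals.
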